6.2.3.6 Outcome events reported by the investigators

Outcome events using the investigator-reported terms will be summarized by treatment group, using tables analogous to those for adverse events. No statistical testing of these events will be performed, as the adjudicated outcome events are components of the primary, secondary and exploratory efficacy variables.

An overall summary of all outcome events will be generated by treatment group.

The number of subjects with all outcome events, on-treatment outcome events from randomization up to 30 days after stop of study medication, post-treatment outcome events occurring more than 30 days after stop of study drug or after the EOS Visit, outcome events by maximum intensity and outcome events by worst outcome will be summarized by treatment group using MedDRA terms grouped by Primary System Organ Class and Preferred Term.

The incidence rate of outcome events per 100 patient-years will also be provided by treatment group using MedDRA terms grouped by Primary System Organ Class and Preferred Term. The time under risk for the incidence rates is defined as the time from randomization until the first onset of the event or the last date of contact with the subject in case no such event is recorded.

Outcome events will be listed separately in the section 14.2 tables.

6.2.4 Supportive efficacy analyses to account for the COVID-19 pandemic

Supportive analyses to evaluate the impact of the COVID-19 pandemic on the primary analysis will be conducted for primary and secondary time-to-event endpoints. No supportive

analyses are required for the secondary endpoint “change in UACR at Month 4 to baseline” because Visit 3 (Month 4) took place for all subjects at the latest in mid 2019 and thus before the onset of the COVID-19 pandemic.

The primary analysis of the primary and secondary time-to-event endpoints mostly follows the treatment policy strategy as described in the ICH E9 (R1) [9], in which subjects are analyzed as they were intended to be treated and all adjudicated endpoint events are counted disregarding any previous intercurrent events like COVID-19 infections or study drug interruptions which could have an influence on the occurrence of the event of interest. Only the competing event of death for other causes (non-CV or non-renal) is treated with a while-alive strategy by measuring the effect until the subject died for other causes. This general approach is still considered valid, considering the following factors:

- Pandemic-related study disruptions are expected to be equally likely to occur in either treatment group, therefore not creating bias for the treatment effect.
- The first subject was randomized in October 2015, and randomization was completed approximately one year before the onset of the COVID-19 pandemic in January 2019. Thus, subjects could have been in the trial for up to ~4 years unaffected by the pandemic.
- Information on most adjudicated endpoint events can still be collected even when physical visits cannot take place although incidences or reporting of some adjudicated events might change, e.g. as fewer subjects might be hospitalized and have a higher risk of death. Moreover, eGFR-based events pose an exception in that they can only be collected at physical visits. However, the possibility of missing eGFR measurements also exists for non-pandemic-related reasons as the CSP allows for physical visits to be replaced by phone contacts if necessary. Final missed eGFR measurements are also captured with the censoring rules of the respective endpoints, see section 6.2.2.1.

To quantify the impact of the COVID-19 pandemic on the primary analysis, a supplemental analysis will be conducted to address the hypothetical scenario in which subjects would have continued with the study as if the COVID-19 pandemic had not taken place. In this analysis, subjects with an event date or censoring date after the onset of the COVID-19 pandemic are re-censored at the onset date of the COVID-19 pandemic.

The above-mentioned analysis will be assessed with the four different versions for the COVID-19 onset date as described in section 4.8.

Figures of the Nelson-Aalen estimates of the cumulative hazard rates for both the primary analysis and each of these supplemental analyses will be supplied to visualize any potential pandemic-induced differences in the time to the respective endpoint event.

Similarly, a supplemental analysis will be conducted for the recurrent-event analysis of hospitalization events by presenting the results of the Andersen-Gill model and the MCF after cutting of time at-risk at each version of the COVID-19 onset date.

Furthermore, the effect of COVID-19 related study disruption on the results of the Cox model including treatment will be investigated in more detail by means of a time-dependent covariate capturing whether the subject is affected by COVID-19 at the respective time, and

by its interaction with treatment. Separate models will be set up with a time-dependent covariate for

- a) the direct impact of COVID-19 adverse events,
- b) any direct or indirect COVID-19 related study disruption.

The impact of the COVID-19 pandemic on the primary and secondary time-to-event endpoints is further analyzed descriptively by summarizing and/or listing

- subjects with a first adjudicated endpoint event before or after the COVID-19 onset date (by any of the four different options described in section 4.8)
- subjects with a first adjudicated endpoint event during a study drug interruption due to COVID-19 vs. due to any reason (where events 30 days after any temporary or permanent stop of study drug are considered)

In addition, the number of subjects affected by the COVID-19 pandemic and experiencing on-treatment investigator-reported outcome events since the country-specific COVID-19 onset date will be summarized by Primary System Organ class and Preferred Term, along with a listing of all investigator-reported outcome events since the country-specific COVID-19 onset date of subjects with a COVID-19 infection.

6.3 Pharmacokinetics/pharmacodynamics

6.3.1 Pharmacokinetics

The plasma concentration versus time data of Visit 3 (Month 4) and at subsequent yearly visits will be evaluated descriptively, separated by dose and visit. Plots will be prepared of all individual plasma concentrations vs. actual relative study times (time of sample collection after time of study drug administration).

Evaluation of the concentration data will be performed using Population PK methods, followed by PK/PD analyses. These analyses will be described in a separate Analysis Plan outside of this document and will be reported separately.

6.3.2 Pharmacodynamics

Not applicable.

6.4 Safety

All analyses on safety and tolerability data will be performed in the SAF.

6.4.1 Adverse events

Adverse events (AEs) will be coded using the Medical Dictionary for Regulatory Activities (MedDRA, latest version available prior to data base freeze). A listing will be provided linking the original investigator terms and the coded terms. AEs will also be presented grouped by SMQs.

AEs that started or worsened after the first dose of study drug up to 3 days after any temporary or permanent interruption of study drug will be considered as treatment emergent AEs (TEAEs).

An overall summary of all AEs and TEAEs will be generated by treatment group.

The number of subjects with TEAEs, pre-randomization AEs, post-treatment AEs occurring more than 3 days after any temporary or permanent stop of study drug, treatment-emergent SAEs, treatment-emergent study drug-related AEs, treatment-emergent study drug-related SAEs, treatment-emergent SAEs and TEAEs causing permanent discontinuation of study drug, treatment-emergent non-serious AEs, non-serious AEs, TEAEs by maximum intensity, treatment-emergent SAEs by maximum intensity, drug-related TEAEs by maximum intensity, TEAEs by worst outcome and treatment-emergent SAEs by worst outcome will be summarized by treatment group using MedDRA terms grouped by Primary System Organ Class and Preferred Term.

To comply with local regulatory requirements in Japan, some cardiovascular disease-related outcome events will also be documented as (S)AEs in Japan. These will be included in the outcome event tables (see section 6.2.3.6), and to avoid double-counting of such events, they will not be included in the adverse event summary tables or listings. A separate listing will be generated for all AEs excluded from the AE analysis due to double reporting in Japan.

In case of events with different intensity within a subject, the maximum reported intensity will be used. If intensity is missing, the event will be considered as severe. If the same event is considered as both unrelated and related to the study drug within a subject, the event will be reported as related to study drug. If the drug relationship is missing, the event will be considered as being related to the study drug.

These further safety variables are listed in section 10.3.4 of the protocol:

- Number of subjects with hospitalization for hyperkalemia
- Number of subjects discontinuing study drug permanently due to hyperkalemia
- Number of subjects with hospitalization for worsening of renal function
- Number of subjects discontinuing study drug permanently due to worsening of renal function

These will be summarized by treatment group using frequency counts. For the number of subjects with these events, the summary will be provided once for all events and once for all treatment-emergent events.

Cumulative incidences based on Aalen-Johansen estimates (including 95% confidence intervals) [14] and accounting for mortality as competing risk will be provided for the time to first treatment-emergent hyperkalemia event (any, leading to hospitalization and leading to permanent discontinuation of study drug). For this analysis, the person-time at risk for a single subject is the number of days from first intake of study drug until the event of interest or until the minimum of (date of death, last exposure to treatment +3 days) excluding temporary study drug interruptions (i.e. the time between start of a temporary study drug interruption + 3 days until the end of the interruption).

Furthermore, concomitant medications taken as treatment for treatment-emergent hyperkalemia will be shown by treatment group and overall.

Separate tables summarizing TEAEs, study drug-related TEAEs, and SAEs that occurred in more than 5% of the subjects will be provided.

Deaths, SAEs and AEs leading to permanent study drug discontinuation will be listed separately.

In addition, subjects with a COVID-19 adverse event will be summarized and listed. The number of subjects affected by the COVID-19 pandemic and experiencing treatment-emergent adverse events since the country-specific COVID-19 onset date will also be summarized, along with a listing of all adverse events since the country-specific COVID-19 onset date of subjects with a COVID-19 infection.

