10.4 Determination of sample size - amended

This section was changed in Amendment 3, see Section [15.1.2.41](#).

This is an event-driven study. A total of between 970 and 976 primary efficacy endpoint events will have 90% power to demonstrate superiority of finerenone to placebo using a logrank test at a two-sided significance level of 5.0%, assuming a 20% relative risk reduction, i.e. a true hazard ratio of 0.80 (the hazard ratio that will be observed in the study will be different, i.e. closer to 1 due to treatment discontinuations). The study will stop when approximately 976 primary efficacy endpoints accrue across both treatment arms.

With an assumed treatment duration of between 44 and 48 months (duration of recruitment period: 33 and 41 months, equal recruitment pattern during the accrual period, maximum treatment period of the last subject recruited: 11 and 7 months, respectively), the planned total number of subjects to be randomized is estimated to be between 6212 and 6286 subjects, respectively, assuming an annual placebo event rate of 8%, a common annual lost-to-follow-up rate of 0.7% in both treatment groups, an annual finerenone discontinuation rate of 5% and assuming that placebo discontinuation will not change the hazard. 6400 subjects are planned to be randomized taking a certain ramp-up during recruitment into account. Assuming a screening failure rate of 50%, 12800 subjects are planned to be screened.

Due to the minimal effect of the interim analysis on the overall power of the study, an adjustment of sample size would be negligible.

The assumption of the annual placebo event rate of 8% is based on the results from the MICRO-HOPE, RENAAL, IDNT, ALTITUDE and SAVOR-TIMI 53 trials. The latter 2 are more recent studies. Event rates were obtained from the respective studies in the arms where treatment would more closely resemble that in the placebo population of the CV-DKD study who will be on standard of care treatment for DKD. Annual event rates for the composite CV endpoint range from 7-10% for older studies and 5-6% for more recent studies. As the anticipated population study 17530 will be more enriched for CV outcomes than ALTITUDE and SAVOR-TIMI 53, a likely lower mean eGFR and higher median UACR value, the assumed annual placebo event rate of 8% is assumed to be appropriate for this Phase III setting ([10](#), [11](#), [51-54](#)).

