In the same way described for treatment-emergent hyperkalemia AEs in section 6.4.1, cumulative incidences based on Aalen-Johansen estimates (including 95% confidence intervals) [14] and accounting for mortality as competing risk will be provided for the time to treatment-emergent serum potassium value >5.5 or 6.0 mmol/L. For this analysis, the person-time at risk for a single subject is the number of days from first intake of study drug until the event of interest or until the minimum of (date of death, last exposure to treatment +3 days) excluding temporary study drug interruptions (i.e. the time between start of a temporary study drug interruption + 3 days until the end of the interruption).

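### The hyperkalaemia curves count only death as a competing event, so permanent discontinuation for other reasons is in effect censored: an error for the curve of stopping drug because of hyperkalaemia, and an unstated estimand for the others

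*SAP*

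**What the plan says.** SAP 6.4.1 says of its Aalen-Johansen cumulative incidences that estimates "accounting for mortality as competing risk will be provided for the time to first treatment-emergent hyperkalemia event". Three hyperkalaemia endpoints are covered: "any, leading to hospitalization and leading to permanent discontinuation of study drug". Each subject's time at risk starts at first intake and runs to the event or "until the minimum of (date of death, last exposure to treatment +3 days) excluding temporary study drug interruptions".

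SAP 6.4.2 extends this to central-laboratory potassium above 5.5 or 6.0 mmol/L, "In the same way described for treatment-emergent hyperkalemia AEs in section 6.4.1", with the same at-risk rule and again "accounting for mortality as competing risk will be provided for the time to treatment-emergent serum potassium value".

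SAP 6.4.1 also fixes what can count: an adverse event is treatment-emergent only if it starts or worsens after the first dose and "up to 3 days after any temporary or permanent interruption of study drug". Beside the curves, the SAP plans crude summaries of hospitalization and permanent discontinuation for hyperkalaemia: "These will be summarized by treatment group using frequency counts".

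Neither section says how a subject who stops drug permanently for another reason is coded. With death the only competing event and time at risk closed at last dose plus 3 days, censoring is the only handling left, although the SAP does not use that word here.

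**The concern.** The Aalen-Johansen estimator redistributes a censored subject's probability as if that subject could still have the event. After permanent discontinuation plus 3 days, that is impossible under the SAP's own definition of treatment-emergence, just as it is after death. The plan allows for one event that rules out the outcome and not for the other.

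The difficulty is sharpest for the curve of stopping drug permanently because of hyperkalaemia. A subject who has already stopped for another reason cannot stop again, so the two reasons are rival causes of one event.

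These curves give the time course of absolute risk for a harm that Protocol 9.7.1 names among the main ones seen with this drug class, finerenone included. A reader will take them as the chance that a treated patient has the event by a given time.

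**Working it through.** **The plan's own figure.** The documents give no figure for these curves. The only stated result that uses the discontinuation rate is the event target in Protocol 10.4: 970 events with 6212 subjects, or 976 with 6286, which assumes "an annual finerenone discontinuation rate of 5" per cent. Without dilution, Schoenfeld's formula gives 4(1.960 + 1.282)²/(ln 0.80)² = 844.1, so 845 events. A log-rank calculation with uniform accrual, an 8% yearly placebo event rate, hazard ratio 0.80, 0.7% yearly loss and 5% yearly finerenone discontinuation reverting to the placebo hazard gives 972 events and 6230 subjects (33 + 11 months), or 978 and 6305 (41 + 7 months). The target is reproduced, so 5% is the plan's working rate. It implies 1 − 0.95^(44/12) = 17.1% off drug by 44 months and 1 − 0.95^4 = 18.5% by 48 months.

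**Inputs.**
- d = 0.05 per year, permanent discontinuation (Protocol 10.4, finerenone, all reasons).
- T = 2 and 4 years (Protocol 10.4 plans 44 to 48 months).
- Assumed, not in the documents: death m = 0.02 per year (range 0.01 to 0.04); event hazards h = 0.05 for any hyperkalaemia, 0.005 for hospitalization and 0.003 for discontinuation because of it; all hazards constant and independent.

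**Formulas.**
- Planned (discontinuation censored): h/(h+m) × [1 − exp(−(h+m)T)]
- Discontinuation competing: h/(h+m+d) × [1 − exp(−(h+m+d)T)]

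For any hyperkalaemia at 4 years the planned version is 0.05/0.07 × (1 − e^−0.28) = 17.44%, and the competing version is 0.05/0.12 × (1 − e^−0.48) = 15.88%.

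| Endpoint (assumed h) | T | Planned | Competing | Gap, points | Relative excess |
|---|---|---|---|---|---|
| Any (0.05) | 2 y | 9.33% | 8.89% | 0.44 | 5.0% |
| Any (0.05) | 4 y | 17.44% | 15.88% | 1.56 | 9.8% |
| Hospitalization (0.005) | 4 y | 1.90% | 1.73% | 0.18 | 10.1% |
| Discontinuation (0.003) | 2 y | 0.59% | 0.56% | 0.03 | 5.0% |
| Discontinuation (0.003) | 4 y | 1.15% | 1.04% | 0.11 | 10.2% |

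**Sensitivity at 4 years.**
- Death at 1%, 2% and 4% a year leaves the excess for the rarest endpoint at 10.2%, 10.2% and 10.0%.
- With 3% yearly discontinuation for other reasons, the excess is about 6%.
- The protocol's 5% covers all reasons, so stops for hyperkalaemia should come out of it. With h = 0.003 and d = 0.047 the excess is 9.5%. With h = 0.006 it falls from 10.1% (2.28% against 2.07%, d = 0.05) to 8.9% (2.28% against 2.09%, d = 0.044).

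**Check by simulation.** An Aalen-Johansen estimator on 200,000 simulated subjects with staggered entry gave, near the end of follow-up, 9.0-9.6% for any hyperkalaemia (h = 0.05) and 9.5-9.8% for a rare endpoint (h = 0.005).

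**Comparison with death.** Ignoring death altogether would inflate the rarest endpoint at 4 years by 2.0%, 4.0% or 8.2% at 1%, 2% or 4% yearly mortality.

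**The case against.** The strongest reply is that the curves target risk while exposed. Temporary interruptions are cut out of the time at risk, so the axis is time on drug, and closing follow-up shortly after the last dose is a recognised choice for that target. This stands as a coherent reading for any hyperkalaemia and for the potassium curves. It needs discontinuation to be independent of hyperkalaemia risk, and the SAP does not state this target, although its section 6.2.4 names estimand strategies for the efficacy endpoints.

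The reply does not rescue the curve for stopping because of hyperkalaemia, since its risk if nobody stopped for any other reason is not what a reader would take from it. It is also doubtful for hospitalization. A subject who stops after hyperkalaemia that did not need admission is censored for a reason tied to the outcome, and Protocol 9.7.1 foresees permanent stopping for recurrent hyperkalaemia.

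A second reply is that crude counts and, for potassium, crude percentages with treatment comparisons are already planned and do not have this problem. That is true, and the between-arm tests rest on those percentages. Under staggered entry, however, they do not replace a curve. In the simulation with 33 months' recruitment and 11 months' further follow-up, the crude proportion for any hyperkalaemia was 9.9%, against 14.7% (competing) and 16.0% (censored) on the curves.

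Third, treating discontinuation as competing has its own drawback: an arm with more stopping shows lower incidence at the same on-drug hazard, which in a safety display can hide harm. This also stands, and it is the reason to show both versions.

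**Conclusion.** The point holds in a limited form. As estimates of the actual on-treatment probability, the planned curves are too high by about 5% relative at 2 years and 9-10% at 4 years. This rests on the protocol's 5% yearly discontinuation, constant independent hazards and an assumed mortality near 2% a year, to which the result is insensitive. For the curve of stopping because of hyperkalaemia, the set of competing events is wrong. For the other curves, the fault is that the target is not stated.

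A reader might infer more than the documents support:
- That the inflation is greatest for the discontinuation curve. It is not: the relative excess is 9.8-10.2% across the endpoints, and the absolute gap is smallest there (0.11 points, against 1.56 for any hyperkalaemia).
- That discontinuation is shown to be the larger competing event. It is plausible over the assumed 1-4% mortality range, but the documents give no mortality rate.
- That the arms are distorted by different amounts. This is possible, but no placebo discontinuation rate is given.

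The effect is modest, the display is exploratory, and no hypothesis test uses it. It merits correction because hyperkalaemia is a main identified harm and the change is small.

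**What to change.** In SAP 6.4.1, for the curve of permanent discontinuation because of hyperkalaemia, code permanent discontinuation for any other reason as a competing event together with death.

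For any hyperkalaemia, hyperkalaemia with hospitalization, and potassium above 5.5 and 6.0 mmol/L (6.4.1 and 6.4.2), state the estimand. Show the version with discontinuation as competing beside the planned censored version.

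In all curves, state that subjects still on drug at the end-of-study visit, and subjects lost to follow-up while on drug, are censored administratively. Protocol 10.4 assumes 0.7% yearly loss, so the second group needs a rule.

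The cost is one more event code in the same procedure, a sentence or two in each section, and a second set of curves. The competing-event curve describes risk under the observed pattern of discontinuation, not under continued treatment, and its caption should say so.

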6.4.2 Laboratory parameters

The number of subjects with treatment-emergent (until 3 days after any temporary or permanent interruption of study drug) abnormal laboratory values above or below the normal range will be tabulated by the laboratory parameter and treatment group.

Summary statistics including changes to baseline will be calculated by treatment group and visit for all quantitative laboratory parameters, e.g. for hematology, HbA1c, clinical chemistry and urinalysis. Geometric statistics and ratios to baseline will be presented for creatinine and UACR instead of arithmetic statistics with changes from baseline. For eGFR the relative change will be displayed in addition to the absolute change from baseline.

Summary statistics for serum potassium, eGFR and serum creatinine will also be repeated by treatment group and visit separately for the following subgroups:

- eGFR category at baseline (eGFR <30, 30 to <60, 60 to <90 and ≥ 90 mL/min/1.73m²)
- Baseline serum potassium value (≤ 4.8 mmol/L, >4.8 to 5.0 mmol/L, >5.0 mmol/L)

The following special safety parameters will be further assessed by displaying the number of subjects with treatment-emergent safety events. This will also be performed by visit and by stratification factors. The summaries will be performed for the number of subjects with:

- Absolute value of serum potassium >5.5 mmol/L and >6.0 mmol/L,
- Relative decrease from baseline in eGFR of $\geq 30\%$, $\geq 40\%$, $\geq 50\%$ and $\geq 57\%$
- Absolute value of eGFR <30 mL/min/1.73m².

The percentage of subjects with the respective treatment-emergent events (non-stratified) will be compared between the finerenone and the placebo or active control group by applying separate explorative χ^2 tests with continuity correction. If the expected number of subjects in at least 1 cell of the 2x2 contingency table is less than 5 (see reference 5), Fisher's exact test will be applied instead of the χ^2 test. Estimates and two-sided 95% confidence intervals will be provided for each treatment group and the treatment differences. Clopper Pearson confidence intervals will be calculated for each treatment group, while for treatment differences, due to the computational burden of exact unconditional confidence limits, the Wald asymptotic confidence limits will be calculated.

In the same way described for treatment-emergent hyperkalemia AEs in section 6.4.1, cumulative incidences based on Aalen-Johansen estimates (including 95% confidence intervals) [14] and accounting for mortality as competing risk will be provided for the time to treatment-emergent serum potassium value >5.5 or 6.0 mmol/L. For this analysis, the person-time at risk for a single subject is the number of days from first intake of study drug until the event of interest or until the minimum of (date of death, last exposure to treatment +3 days) excluding temporary study drug interruptions (i.e. the time between start of a temporary study drug interruption + 3 days until the end of the interruption).

